1.1 Study Design

This Phase 3, multinational, randomized, double-blind study is designed to compare the efficacy and safety of the combination of ibrutinib and venetoclax vs. ibrutinib and placebo in R/R subjects with MCL.

Approximately 287 subjects with R/R MCL (up to 27 SRI [Safety Run-in] subjects and 260 randomized subjects) will be enrolled.

A separate open-label cohort is designed to explore the efficacy and safety of the combination of ibrutinib and venetoclax in approximately 75 subjects with TN MCL (approximately 50 subjects \geq 65 years of age and approximately 25 subjects with a TP53 mutation). There will be no Safety Run-in period for this cohort.

1.1.1 Safety Run-in Period

The study will start with an open-label SRI period for subjects with R/R MCL to evaluate the occurrence of Tumor Lysis Syndrome (TLS) and dose-limiting toxicities (DLTs) with the concurrent administration of ibrutinib and venetoclax. The TLS and DLT occurrence will be assessed during the venetoclax Ramp-up Period for a minimum of 5 weeks (Figure 1). Up to 27 subjects may be enrolled during the SRI period.

Venetoclax

Week 4

Week 5 onwards

Week 2

Week 1

20 mg

100 mg

200 mg

Ibrutinib 560 mg once daily

Figure 1. Standard Ramp-up Schedule

1.1.2 Randomization Phase

The Randomization Phase of the study will follow a randomized, double-blind design. Ibrutinib and venetoclax/placebo will be administered using the Standard Ramp-up Schedule (without ibrutinib lead-in) that was determined to be appropriate for each TLS risk category in the Safety Run-in Phase. The Independent Data Monitoring Committee (IDMC) will review the safety recommendations made by the Safety Review Committee (SRC) and will be responsible for giving recommendations on continuing, modifying, or stopping the Randomization Phase of the study.

Subject eligibility will be determined up to 28 days prior to randomization. Approximately 260 eligible subjects will be randomized at a 1:1 ratio to ibrutinib and venetoclax or ibrutinib and placebo. Randomization will be stratified by number of prior lines of therapy, ECOG performance status (PS), and by TLS risk category through the Interactive Response Technology (IRT).

Initially, subjects at increased risk of TLS will be hospitalized for a minimum of 24 hours (and up to 48 hours at the discretion of the investigator) at the start of the 20 mg venetoclax ramp-up dose, and again at the start of the 50 mg venetoclax ramp-up dose for monitoring and prophylaxis of TLS. The IDMC will review unblinded safety data during the course of the study to determine whether continued hospitalization of these subjects during ramp-up remains warranted.

The IDMC will review unblinded safety data including all deaths and any progression associated with safety 6-9 months after the initiation of the Randomization Phase to evaluate the safety of the combination of ibrutinib and venetoclax/placebo and to confirm that continued dosing with the combination is warranted. In addition, the IDMC will review TLS data during the course of

the study to ascertain whether the continued hospitalization of subjects with high tumor burden and/or creatinine clearance <60 mL/min during ramp-up is needed. The composition of the IDMC, responsibilities, authorities, and procedures are detailed in a separate IDMC charter.

1.1.3 Treatment Time and Follow-up Time

Safety Run-in subjects and TN subjects will be treated with ibrutinib and venetoclax, and randomized subjects will be treated with ibrutinib and venetoclax or ibrutinib and placebo for approximately 104 weeks followed by ibrutinib monotherapy on both treatment arms until progressive disease (PD), unacceptable toxicity or withdrawal of consent. Venetoclax and placebo will be discontinued after 104 weeks of treatment regardless of response assessment.

All enrolled subjects who discontinue study treatment for any reason will be followed for progression (if they have not progressed before treatment discontinuation), subsequent anticancer therapy and survival status until study closure.

1.2 Endpoints

Randomized Subjects	Safety Run-in Subjects	
Primary Efficacy Endpoint	Efficacy Assessments	
Progression-free survival (PFS) per investigator	• Overall response rate (ORR) and Duration	
assessment	of Response (DOR) per investigator	
Secondary Efficacy Endpoints	assessment	
Complete response rate (CRR) per investigator assessment	 Progression-free survival per investigator assessment 	
Overall Response Rate (ORR) per investigator assessment	Overall Survival (OS)	
Minimal residual disease (MRD)-negative		
remission rate in subjects who achieve CR per		
investigator assessment and are MRD-positive at		
baseline		
Overall Survival (OS)		
• Time to next treatment (TTNT)		
• Time to worsening in FACT-Lym subscale of the		
health-related quality-of-life questionnaire		
(FACT-Lym)		
Exploratory Endpoint		
PFS based on investigator assessment after		
initiation of subsequent anti-cancer therapy		
(PFS2)		
Safety Assessments	Safety Assessments	
Frequency, severity, and relatedness of AEs	 Frequency of TLS and DLTs 	
Frequency, severity and management of TLS		

Randomized Subjects	Safety Run-in Subjects	
Frequency of AEs requiring discontinuation of study drug or dose reductions, or leading to death	 Frequency, severity, and relatedness of AEs Frequency of AEs causing study drug discontinuation, or dose reductions or leading to death 	
Overall disease assessment is according to Revised Response Criteria for Malignant Lymphoma (Cheson 2014, Lugano Classification Criteria)		

1.3 Statistical Hypotheses

The statistical hypotheses for the primary endpoint (PFS) can be written as follows:

 H_0 : $S_E(t) = S_C(t)$, for all t > 0, where $S_E(t)$, and $S_C(t)$ are survival functions for the experimental and control arms, respectively at all time points t:

VS.

 H_1 : The PFS distribution of the experimental treatment group, $S_E(t)$, is stochastically larger than the control group, $S_C(t)$, with strict inequality for some time point t:

$$S_E(t) \ge S_C(t)$$
 for all $t \ge 0$, and $S_E(t) > S_C(t)$ for some $t > 0$

These hypotheses will be tested for the primary endpoint using a two-sided stratified log-rank test at an alpha level specified in Section 1.6. The source of the stratification factors will be based on IRT data.

1.4 Sample Size Determination

1.4.1 PFS

The Randomization Phase sample size is powered based on the primary endpoint of PFS. Approximately 260 subjects will be randomized at a 1:1 ratio to the ibrutinib + venetoclax arm and the ibrutinib + placebo arm. The calculations are based on the following assumptions using EAST software Version 6.4.1:

- Target hazard ratio is 0.61, which corresponds to an improvement of 9 months in median PFS (mPFS) from 14 months to 23 months for the ibrutinib + venetoclax arm compared to the ibrutinib + placebo arm.
- A total of 134 PFS events will provide approximately 80% power at a one-sided significance level of 0.025 for the study. No interim analysis (IA) is planned for PFS.

Page 11 of 35

• Assuming an enrollment rate of approximately 10-11 subjects per month, the accrual is projected to complete approximately 21 months from the first subject in. The actual length of the study and the time to the primary analysis will depend on the actual enrollment rate and the number of events that occur.

1.4.2 OS

- Target hazard ratio is 0.65, which corresponds to an improvement of ~16 months in median OS (mOS) from 30 months to 46.2 months for the ibrutinib + venetoclax arm compared to the ibrutinib + placebo arm.
- A total of 155 OS events would provide ~76% power at a one-sided significance level of 0.025 adjusting for one interim analysis based on group sequential design with Lan-DeMets spending function with O'Brien-Fleming¹ boundary.
- It is anticipated that 112 and 155 OS events will be observed at the interim analysis (at ~40 months corresponding to the timing of the primary PFS analysis) and at the final analysis (at ~57 months), respectively. The level of significance for each analysis is described in Section 1.6.2.
- The calculation for OS is based on a log-rank test using EAST software version 6.5.

1.5 Planned Analysis

The effect size (HR) assumptions of PFS and OS did not consider potential impact of COVID-19 deaths when the study was initiated. In alignment with the FDA guidance² (Statistical Considerations for Clinical Trials During the COVID-19 Public Health Emergency, June 2020), in order to mitigate the potential impact on the key efficacy endpoints due to COVID-19, the follow-up will be extended to accrue more events as described in Section 1.5.1 and Section 1.5.2 below than the originally planned event numbers (134 events for PFS and 155 events for OS).

1.5.1 Primary PFS Analysis and Interim OS Analysis

The primary PFS analysis will be conducted after approximately 150 PFS events have been observed. No interim analysis is planned for PFS.

An interim analysis (IA) is planned for OS at the time of the primary PFS analysis.

1.5.2 Final OS Analysis

The final OS analysis will be conducted after the last subject was followed for at least 5 years or approximately 170 OS events are observed, whichever occurs first.

At the time of the final OS analysis, a CSR addendum will be provided.

1.6 Testing Procedure and Level of Significance

1.6.1 Adjustment of Multiplicity for Multiple Endpoints:

The one-sided Type I Family Wise Error Rate (FWER) will be controlled at 0.025 by a closed testing procedure for testing the primary endpoint (PFS) and key secondary endpoints. The following key secondary endpoints will be tested only if the primary endpoint (PFS) reaches statistical significance (1-sided 0.025) and will be ranked and tested at 1-sided statistical significance of 0.025 sequentially in the hierarchical order below:

- 1) CR rate per investigator assessment
- 2) Time to next treatment*
- 3) OS
- 4) ORR per investigator assessment

A secondary endpoint with a lower rank cannot be tested until the preceding endpoint achieves statistical significance.

*For US regulatory purposes, time to next treatment will be tested after OS as the third endpoint in the hierarchical order.

At the time of the primary PFS analysis, an interim analysis is planned for OS. Statistical significance level for each OS analysis is described in Section 1.6.2. ORR will be tested at 1-sided 0.025 using the primary PFS analysis data cut when OS significance is achieved.

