1.6.2 Adjustment of Multiplicity for Multiple OS Analyses

To maintain a 1-sided overall significance level of 0.025 for OS, assuming the final OS analysis is based on 170 events, the significance level of the OS final analysis will be adjusted for the OS interim analysis as follows based on Haybittle-Peto boundary instead of O'Brien Fleming boundary as specified in the protocol (Protocol Section 10.3). The actual boundary for the OS final analysis will be based on actual number of OS events at the time of the OS final analysis.

Analysis	# of OS Events	Significance level (1-sided p-value)	Observed Hazard Ratio/Superiority Boundary
IA	Agnostic to number of events	0.0005	< 0.550
FA	170 (assumed)	0.024983	< 0.740

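### In the US testing order, SAP 1.6.1 gives two conflicting conditions for testing ORR and names no data cut for TTNT, so control at one-sided 0.025 depends on how the text is read

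*SAP*

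**What the plan says.** All the testing rules are in SAP 1.6.

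- **Claim (1.6.1):** "The one-sided Type I Family Wise Error Rate (FWER) will be controlled at 0.025 by a closed testing procedure".
- **Order (1.6.1):** after PFS, the listed order is CR rate, TTNT, OS, ORR. A footnote changes it: "For US regulatory purposes, time to next treatment will be tested after OS as the third endpoint in the hierarchical order". The US order is therefore CR rate, OS, TTNT, ORR.
- **Rank rule (1.6.1):** "A secondary endpoint with a lower rank cannot be tested until the preceding endpoint achieves statistical significance".
- **ORR rule (1.6.1):** "ORR will be tested at 1-sided 0.025 using the primary PFS analysis data cut when OS significance is achieved". It does not mention TTNT and has no US version.
- **Two OS tests:** SAP 1.5.1 states "An interim analysis (IA) is planned for OS at the time of the primary PFS analysis". SAP 1.5.2 places the final OS analysis "after the last subject was followed for at least 5 years or approximately 170 OS events are observed, whichever occurs first".
- **OS levels (1.6.2):** the interim row reads "Agnostic to number of events 0.0005 < 0.550" and the final row "170 (assumed) 0.024983 < 0.740".

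No section names a data cut for TTNT. Table 2 in SAP 4.2 gives it the PFS analysis method and nothing on timing.

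**The concern.** A fixed-sequence procedure keeps its familywise level on two conditions: each endpoint is released only by success of the one before it, and each is tested on data fixed in advance (or with its own alpha spending). The US order raises a question on both.

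**Release of ORR.** Suppose OS is significant and TTNT is not. The rank rule says that ORR may not be tested. The ORR sentence, taken literally, says that it is tested at 0.025. A confirmatory plan should not leave that choice open until the results are known.

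**Data for TTNT.** In the US order TTNT can be released at the interim or at the final OS analysis. The SAP settles the equivalent question for ORR by fixing the primary PFS cut. It does not do so for TTNT, the other endpoint in that position. If the cut followed the OS result, the look at which TTNT is tested would depend on data correlated with TTNT, and a full 0.025 test would not keep its level.

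At stake is the status of US claims on TTNT and ORR.

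**Working it through.** **1. The plan's own OS figures.** One-sided 0.0005 gives z = 3.2905; one-sided 0.024983 gives z = 1.9603. With 1:1 allocation the HR boundary is exp(-2z/√d) for d deaths.

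- Interim: HR 0.550 implies d = (2 × 3.2905 / ln(1/0.550))² = 121 deaths. SAP 1.4.2 anticipated 112.
- Final: exp(-2 × 1.9603/√170) = 0.740, as stated.
- Total OS alpha: 0.0005 + P(Z₁ < 3.2905, Z₂ > 1.9603), with correlation √(121/170), is 0.0250.

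The OS boundaries are sound. The question is only what OS success releases.

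**2. ORR under each rule in the US order, with OS significant:**

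| TTNT result | Rank rule | ORR sentence read literally |
|---|---|---|
| Significant | ORR tested | ORR tested |
| Not significant | ORR not tested | ORR tested |

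The rules differ only in the second row.

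**3. Error if the ORR sentence were followed.** Take PFS, CR rate and OS as real effects that succeed, with TTNT and ORR both null and each tested at 0.025. The chance of at least one false claim is 1 - Φ₂(1.960, 1.960; r), where Φ₂ is the bivariate normal distribution function. The documents give no correlation r, so a range is assumed.

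| r | Familywise error |
|---|---|
| 0 | 1 - 0.975² = 4.94% |
| 0.3 | 4.76% |
| 0.5 | 4.54% |

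Under the rank rule ORR needs TTNT to succeed first, so the error is at most 2.5%.

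**4. Error if TTNT were tested at whichever OS analysis succeeds.** Inputs: OS HR 0.65 (SAP 1.4.2), final analysis at 170 deaths, interim at 112 or 121. Assumed: TTNT null, TTNT information fraction equal to that of OS, and a common OS-TTNT correlation ρ.

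- Mean of the final OS statistic: ln(1/0.65) × √170 / 2 = 0.4308 × 13.038 / 2 = 2.808.
- Mean at interim: 2.808 × √(112/170) = 2.279, or 2.808 × √(121/170) = 2.369.
- Chance that OS crosses at interim: 1 - Φ(3.291 - 2.279) = 15.6%, or 1 - Φ(3.291 - 2.369) = 17.8%. On these assumptions US TTNT would usually open only at the final OS analysis, or not at all.
- TTNT error = P(Z₁ > 3.291, T₁ > 1.960) + P(Z₁ ≤ 3.291, Z₂ > 1.960, T₂ > 1.960), where Z is OS, T is TTNT, and 1 and 2 are interim and final.

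| ρ | 112 interim deaths | 121 interim deaths |
|---|---|---|
| 0.3 | 2.5% | 2.5% |
| 0.5 | 2.7% | 2.7% |
| 0.7 | 2.9% | 2.8% |
| 0.9 | 2.9% | 2.8% |
| 0.99 | 2.7% | 2.6% |

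Taking instead the least favourable OS effect at each ρ, the maximum runs from 2.7% (ρ = 0.5) to 3.5-3.6% (ρ = 0.99).

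**5. With one fixed cut.** If TTNT is null and is tested once on a prespecified cut, P(OS and TTNT both significant) ≤ P(TTNT significant) = 2.5%, whichever OS analysis opens it. With ORR conditional on TTNT, the whole chain is held at 0.025.

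**The case against.** A reader might infer that the SAP releases ORR on OS success alone. It does not say that. The rank rule stands in the same subsection, under a declared closed testing procedure, and nothing says that the ORR sentence overrides it. OS significance can fairly be read as a necessary condition, in a sentence whose main job is to fix ORR's level and data cut when OS succeeds late. On that reading the 4.5-4.9% does not arise. This stands, and it is why the point is a contradiction to be resolved and not a demonstrated loss of control.

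A reader might also infer that the SAP prescribes testing TTNT at whichever OS analysis succeeds. That would be an inference from silence. SAP 1.6.2 provides multiple analyses for OS only, and a single TTNT test on the primary cut is an equally natural reading, with error at most 2.5%. The SAP names no TTNT cut for the non-US order either, but there TTNT precedes OS and does not wait for a twice-tested endpoint.

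Finally, it is tempting to add that a late US TTNT test would absorb treatment decisions made after unblinding. The documents do not support this: Protocol 5.1.2.2 and SAP 1.7.1 keep subjects, investigators and the study team blinded, and no unblinding at the primary analysis is described.

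What survives is that the ORR-specific rule and the rank rule give opposite answers in one US scenario, and that the US TTNT cut is unstated.

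**Conclusion.** The point holds as a conflict in a stated decision rule plus a gap, both confined to the US order. Read with the rank rule governing and TTNT tested once on the primary PFS cut, the US chain keeps 0.025. Read with the ORR sentence governing, the familywise error could be about 4.5-4.9% when TTNT and ORR are both null (assumed correlations 0-0.5). Read with TTNT tested at whichever OS analysis succeeds, the TTNT error is about 2.6-2.9% at OS HR 0.65 with 112-121 interim deaths (assumed correlations 0.5-0.99), which is a modest excess. All correlations and the TTNT information fraction are assumptions. The text as it stands does not say which reading applies, so the stated 0.025 is not assured for US claims on TTNT and ORR. The primary PFS test, CR rate, both OS boundaries and the non-US hierarchy are unaffected.

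**What to change.** Before unblinding, replace the ORR sentence in SAP 1.6.1 with one that covers both orders, for example: *Once OS is significant at either analysis, the endpoints ranked below it are each tested once at 1-sided 0.025 on the primary PFS analysis data cut: non-US, ORR; US, TTNT, then ORR only if TTNT is significant.*

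This removes the conflict, gives US TTNT the same cut as ORR and bounds the chain at 0.025. No boundary or event target changes. The cost is one sentence, and US TTNT would be tested with less follow-up than it would have at the final OS analysis. Longer TTNT follow-up can still be reported descriptively.

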1.6.2 Adjustment of Multiplicity for Multiple OS Analyses

To maintain a 1-sided overall significance level of 0.025 for OS, assuming the final OS analysis is based on 170 events, the significance level of the OS final analysis will be adjusted for the OS interim analysis as follows based on Haybittle-Peto boundary instead of O'Brien Fleming boundary as specified in the protocol (Protocol Section 10.3). The actual boundary for the OS final analysis will be based on actual number of OS events at the time of the OS final analysis.

Analysis	# of OS Events	Significance level (1-sided p-value)	Observed Hazard Ratio/Superiority Boundary
IA	Agnostic to number of events	0.0005	< 0.550
FA	170 (assumed)	0.024983	< 0.740

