10.3 Sample Size Determination (Randomization Phase)

The Randomization Phase sample size will be powered based on the primary endpoint of PFS. Approximately 260 subjects will be randomized at a 1:1 ratio.

The null hypothesis is hazard ratio (HR) ≥ 1 for the ibrutinib and venetoclax group relative to ibrutinib and placebo group. The alternative hypothesis is HR ≤ 1 .

With a targeted HR of 0.61 (corresponding to an improvement in median PFS from 14 months to 23 months), 134 PFS events will provide at least 80% power at a 1-sided overall significance level of 0.025. Assuming an enrollment rate of approximately 10-11 subjects per month (a rough estimate based on 3 pieces of enrollment rates), the accrual is projected to complete approximately 21 months from the first subject in. Detailed projection of the enrollment schedule will be provided in a separate document. The actual length of the study and the time to the final analysis will depend on the actual enrollment rate and the number of events that occur.

The sample size and power calculations for the study are based on a 1-sided log-rank test for PFS and were calculated using the software package, East 6.4.1 (Cytel Software Corp, Cambridge, MA).

OS will be analyzed at the time of the primary analysis of PFS when the superiority boundary for PFS is crossed. It is anticipated that 112 and 155 OS events in total will be observed at the interim analysis (at ~40 months) and at the final analysis (at ~57 months), respectively. This is based on the assumption that the median OS for the ibrutinib and placebo group is approximately 30 months (estimated based on data from subjects treated with ibrutinib monotherapy in MCL3001), and the hazard ratio is 0.65 (corresponding to a median OS of 46.2 months for the ibrutinib and venetoclax group). With 155 OS events, the study has ~76% power at a 1-sided overall significance level of 0.025. At the interim analysis, if 112 OS events are observed, the information fraction will be 72.3%. The 1-sided alpha spending is 0.008 at the interim analysis based on a group sequential design with Lan-Demets spending function with O'Brien-Fleming boundary. This will ensure control of the overall type I error for the study. The exact alpha boundary will be calculated using the actual number of events observed at the interim analysis.

The calculations for OS are based on the software package, East 6.5 (Cytel Software Corp, Cambridge, MA).

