7 CHANGES IN THE PROTOCOL-PLANNED ANALYSES

- 1. In alignment with the FDA guidance (Statistical Considerations for Clinical Trials During the COVID-19 Public Health Emergency, June 2020), in order to mitigate the potential impact on key efficacy endpoints due to COVID-19, the follow-up will be extended to accrue more events as described in Section 1.5.1 and Section 1.5.2 over the originally planned event numbers (134 events for PFS and 155 events for OS).
- 2. Change superiority boundary for the interim OS analysis from O'Brien Fleming boundary to Haybittle-Peto boundary.
- 3. Specify secondary and exploratory endpoints to be included in the CSR.
- 4. IRC will be implemented to do the overall disease assessment based on Cheson 2014 (Lugano Classification Criteria). A sensitivity analysis will be conducted for PFS using the IRC assessment.
- 5. Since only 9 subjects in total were randomized to the stratum of ECOG performance status of 2, stratification by the three randomization stratification factors will lead to empty or very small strata. Therefore, all stratified tests/analyses will only be based on two randomization stratification factors per IRT: prior lines of therapy (1-2 vs ≥ 3) and TLS risk category (low risk vs. increased risk).
- 6. The CR rate and ORR will be compared by rate ratio between the two treatment arms using CMH chi-square test stratified by the two randomization stratification factors instead of by the difference in proportion between the two treatment arms.
- 7. The MRD-negative remission rate for CR subjects evaluable for MRD will be compared by Fisher's Exact test due to the small sample size.

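### Does the fixed hazard ratio of 0.550 in the OS interim row of SAP 1.6.2 contradict that row's claim not to depend on the event count?

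*SAP*

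**What the plan says.** SAP 1.6.2 replaces the protocol's O'Brien-Fleming boundary for OS with a Haybittle-Peto boundary. Its table has two rows:

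| Analysis | OS events | One-sided level | HR boundary |
|---|---|---|---|
| Interim | "Agnostic to number of events" | 0.0005 | <0.550 |
| Final | 170, marked as assumed | 0.024983 | <0.740 |

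The last column is headed "Observed Hazard Ratio/Superiority Boundary". The text adds that the final boundary "will be based on actual number of OS events at the time of the OS final analysis", and it makes no such statement about the interim count.

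Other places bear on the reading:

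- SAP 1.6.1 points to this table for the rule: "Statistical significance level for each OS analysis is described in Section 1.6.2".
- SAP 4.2, Table 2, gives OS the same methods as the primary PFS analysis, which is a stratified log-rank test.
- SAP Section 7, item 2, records the amendment as "Change superiority boundary for the interim OS analysis" and goes on to name O'Brien-Fleming as the old boundary and Haybittle-Peto as the new one.
- Protocol 10.3 says of the interim: "The exact alpha boundary will be calculated using the actual number of events observed at the interim analysis".
- The only interim OS count in either document is 112, in Protocol 10.3 and SAP 1.4.2. It is paired with 155 final events.

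**The concern.** The interim row appears to contradict itself. It disclaims any dependence on the number of deaths, then gives a hazard ratio whose p-value depends on exactly that number. The final row declares its assumed count and the interim row does not. The hazard ratio column carries the words superiority boundary, and Section 7 uses the same words for the interim decision rule, so a reader could take HR <0.550 as the test.

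Away from one particular count the two columns can disagree. With fewer deaths, an observed hazard ratio just under 0.550 would satisfy the printed ratio and miss p = 0.0005; with more deaths the reverse could happen. OS gates the test of overall response rate, and in the US order also time to next treatment, so the answer would carry down the hierarchy.

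The final level raises a second question. It too depends on the interim count, but SAP 1.6.2 mentions only the final count when it promises to update the boundary.

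**Working it through.** **Inputs.** From SAP 1.6.2: interim level 0.0005 (z = 3.2905), final level 0.024983 (z = 1.96025), 170 final deaths, overall one-sided 0.025. From SAP 1.4.1: 1:1 allocation. From SAP 1.4.2: 112 interim deaths under the 155-event plan. The counts of 100, 130 and 150 are assumptions, used only to show a range.

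**Step 1: reproduce the final row.** For a 1:1 log-rank test with d deaths, the hazard ratio equivalent to a critical value z is approximately HR = exp(−2z/√d). At d = 170, exp(−2 × 1.96025/13.038) = 0.7403. The printed 0.740 is right, so this form fits the SAP's table.

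**Step 2: find the count behind 0.550.** Solving for d gives (2 × 3.2905/ln 0.550)² = 121.2. Allowing for rounding (0.5495 to 0.5505) gives 120.8 to 121.5, so 121 is the only whole number that fits.

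**Step 3: check that count against the final level.** Solve P(Z1 > 3.2905 or Z2 > c) = 0.025, with Z1 and Z2 bivariate normal and correlation √(d/170). The final level is 0.024982 for d = 120, 0.024983 for d = 121 and 0.024985 for d = 122. The printed 0.024983 also points to 121. All three printed figures therefore agree at 121 and 170 deaths, and none is miscalculated.

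**Step 4: the effect of another interim count.** The last two columns give total one-sided alpha over both looks when the final level stays at 0.024983.

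| Interim deaths | HR equal to p = 0.0005 | One-sided p at HR 0.550 | Exact final level | Alpha, p-value rule | Alpha, HR <0.550 rule |
|---|---|---|---|---|---|
| 100 | 0.518 | 0.00140 | 0.024937 | 0.025046 | 0.025273 |
| 112 | 0.537 | 0.00078 | 0.024967 | 0.025016 | 0.025052 |
| 121 | 0.550 | 0.00050 | 0.024983 | 0.025000 | 0.025000 |
| 130 | 0.561 | 0.00033 | 0.024993 | 0.024990 | 0.024986 |
| 150 | 0.584 | 0.00013 | 0.025000 | 0.024983 | 0.024983 |

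**Step 5: is 112 the right comparison?** It belongs to the plan with 134 PFS and 155 OS events. SAP 1.5 extends follow-up to accrue more events "than the originally planned event numbers (134 events for PFS and 155 events for OS", and SAP 1.5.1 now places the interim at about 150 PFS events. If the old information fraction is simply carried over to 170 final deaths, 112/155 × 170 ≈ 123, where the equivalent hazard ratio is 0.552. This is a scaling and not a documented projection, but it shows that 121 is a reasonable working count.

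**Step 6: which column decides?** SAP 1.6.1 sends the reader to 1.6.2 for a significance level, and the text of 1.6.2 is about a significance level. A Haybittle-Peto boundary is a fixed, very small p-value at the interim, which is why it can disregard the event count. The test in SAP 4.2 is a stratified log-rank test, which yields a p-value. Read in full, Section 7, item 2 contrasts two boundaries that are both defined through significance levels. Protocol 10.3 also speaks of crossing a superiority boundary for PFS, although neither document gives PFS a hazard ratio boundary, only the one-sided 0.025. In these documents the term does not mean a hazard ratio threshold.

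**The case for a change.** The strongest opposing case is that a pre-specified rule should have one reading before unblinding. No sentence says which column decides, and the term used for the rule in Section 7 heads the hazard ratio column. At 112 deaths an observed ratio between 0.537 and 0.550 would pass one column and fail the other; at 130 deaths a ratio between 0.550 and 0.561 would do the reverse. A hazard ratio translation is common in such tables, but it normally states its event count, and this row implies that none is needed.

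What stands is the missing label: the interim row should have marked about 121 deaths as assumed, as the final row does for 170. The claim of two competing rules does not stand, for the reasons in Step 6. The reported ratio will also come from a stratified Cox model, so its link to the log-rank p-value is only approximate. That is another reason to treat 0.550 as a guide.

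On the final level, the SAP's stated aim is to hold 0.025 over both looks. Recomputing a two-look boundary to that total requires the interim count, which will be known by then. The protocol's commitment to the actual interim count was written for the O'Brien-Fleming plan, but Section 7 lists only the boundary type as changed.

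**Conclusion.** No change to the plan follows; this is a clerical omission. The level of 0.0005 governs the interim OS test and does not depend on the number of deaths. HR <0.550 is its approximate equivalent at an unstated 121 deaths.

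Followed as written, the plan gives a sound result. With the final level left at 0.024983, total one-sided alpha at 112 interim deaths exceeds 0.025 by 0.000016 under the p-value rule. Even under the hazard ratio misreading the excess is 0.000052, and with as few as 100 deaths it is 0.000273. From 121 deaths upward there is no excess under either rule. Recomputing the final level from the actual counts, as the aim of SAP 1.6.2 implies, removes the excess under the p-value rule.

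These figures assume 170 final deaths and the unstratified 1:1 log-rank approximation, so the match between hazard ratio and p-value is approximate. The conclusion that the p-value governs rests on the text of the documents and does not depend on that approximation.
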